o. After completion of the 6 days (144 hours) on the study device, the infant will be switched back to the regular device used in the NICU.

p. While the infant is on the study device during the first 12 hours of the study, a member of the research team will remain at the infant's bedside to make sure the device remains operational, but they will not be allowed to adjust the oxygen concentration. The bedside nurse will be able to switch the device to manual mode anytime she/he feels the oxygen concentration needs to be adjusted faster than the computer is doing in the automatic mode.

q. The study will be stopped earlier if the primary healthcare team feels:

- The infant requires more respiratory support than can be provided by the high flow nasal cannula or bubble CPAP device.
- The infant no longer requires respiratory support and can be weaned off the high flow nasal cannula or bubble CPAP device.

5. Inclusion/Exclusion Criteria

a. Inclusion criteria: infants admitted to the NICU who were less than or equal to 30 weeks gestational age or less than or equal to 1500 grams at birth who are currently on

high flow nasal cannula or bubble CPAP and require at least 2 adjustments to the FiO2 per shift and/or have at least 2 desaturation events per shift.

b. Exclusion criteria: infants admitted to the NICU with congenital heart disease. Infants who are set on a minimum FiO2 set point by their healthcare provider, will also be excluded from this study.

6. Drugs/ Substances/ Devices

The high flow nasal cannula device that we use in the NICU consists of a oxygen blender that is mounted on an IV pole and a Fisher & Paykel Healthcare humidifier that is mounted to the same pole. Medical air and oxygen are introduced in the back of the blender that allows the oxygen concentration to range from 21% (or room air) to 100% oxygen by simply turning the knob on the blender. The flowmeter on the blender is used to adjust the flow of air out of the blender (usually 1-6 lpm). A tube connects the flowmeter with the humidifier where the air is heated and humidified. Another tube then connects the humidifier with the nasal cannula which is placed on the infant's face.

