The study devices are exactly the same set ups as described above except for 3 differences. First, there is a computer attached to the IV pole that accepts input from a pulse oximeter. The computer registers the saturation level and determines if the level is within the prescribed range. Second, there is an attachment between the computer and the knob on the blender. If the oxygen saturation level isn't in the prescribed range, the computer can turn the knob on the blender using this attachment to either increase or decrease the amount of oxygen being delivered to the patient by 2% every 10 seconds as long as the oxygen saturation reading is considered reliable (the heart from the cardiac monitor and the pulse oximeter have to agree within 5 beats per min). Third, the device has an alarm that will sound if the FiO2 is increased or decreased by more than 10% from the baseline FiO2 requirement. For example, if the infant's baseline FiO2 needs were 35% and the FiO2 is increased to 45% while in the automatic mode, an alarm will sound so the nurse can evaluate why the infant is requiring 10% more oxygen than the baseline. The nurse can evaluate the infant to see if the oxygen device is no longer in the infant's nose and reposition it or notify the healthcare providers to have them determine if the infant's condition is deteriorating. If the infant truly needs the extra oxygen, the nurse can reset the baseline oxygen requirement to this new level and the machine will not alarm again until the oxygen level is again 10% out of range. The computer also has a switch that turns it from automatic to manual mode. If the healthcare provider needs to adjust the oxygen concentration faster than the computer is making a change, all they need to do is simply switch the button to manual and they can adjust the knob on the blender to whatever concentration they want.

Name of Medical Device: Automatic Oxygen Control System
Medical Device Description:

The device receives signals with SpO2 information along with the heart rate and respiratory rate. Using the measurements and a set-point, the device determines an FiO2 that is to be applied to a respiratory support system. The device uses a motor to control a blend valve which manipulates the FiO2.

If the device makes inappropriate settings to the FiO2, risk is eliminated since all of the alarms will be in place (as in current practice) and manual control will always be available.

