There will be a total of three replications of the Automatic Oxygen Control System devices at each site. These three devices will be used under the supervision of a study engineer and/or healthcare provider.

There are no known difficulties in using the device.

The cost of the device is funded by the study.

Doctors, respiratory therapists, and nurses will be trained on how to use the device. They will receive training on how to turn the device off and on, switch between automatic and manual modes, and adjust the FiO2 settings on the device. This training will be conducted by the study personnel prior to placing the device on a patient. This training should take less than 5 minutes to complete. A member of the study personnel will be present at the infant's bedside during the first 12 hours of the study period the infant is attached to the device and then 1 hour daily to make sure the device is functioning properly. A member of the study team will also be on-call during the entire study period to answer questions about the device.

The study device will not be documented in the medical records. The study PI and study engineers will be trained in Medical Device Reporting principles.

The study will only last 144 hours. No follow up visits or tests are required.

This device is considered a non-significant risk device requiring no IDE.

7. Study Statistics

a. Primary outcome variable.

- Mean elapsed time needed to re-establish SpO2 within the desired range after an alarm. Does the computer do a better job of keeping the patient in the desired saturation level range compared to the current manual mode? Does the patient return to the prescribed saturation level range quicker in the automatic mode compared to the manual mode?

b. Secondary outcome variables.

- Proportion of time SpO2 is within the prescribed range computed using an area-under-the-curve approach. Is our device safe to use on neonates? Is the transition from automatic to manual mode smooth? Does the device respond appropriately to the patient's saturation level?
- Does the frequency of acute events (apnea, bradycardia and/or desaturation events) decrease if the oxygen saturation level is kept under better control?

- c. Our goal is to enroll 60 patients into the study. We expect to consent 70 subjects to account for drop-out.

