For the safety of every patient in the NICU, we have several redundant systems to monitor our patients. First every patient in the NICU is continuously monitored for their heart rate and respiratory rate. In addition, those infants requiring respiratory support of any type are kept on a pulse oximeter that continuously monitors the patient's oxygen saturation levels. If these vital signs fall out of the prescribed range, the monitor starts to alarm. At the beginning of each shift the nurses make sure the alarms of each of their patients ring on all their babies' monitors through a system known as alarm watch. Additionally, throughout the NICU, monitors are present so healthcare providers can monitor these vital signs in key locations throughout the unit. Furthermore, the heart rate and respiratory alarms ring directly to the nurse's special secure cellular phone used in the hospital that also functions as an alarm monitor so no matter where the nurse may be located in the NICU she can hear these alarms. To protect the confidentiality of the patient's protected health information, the form used to gather the information from the medical record will be coded so the infant's name and medical record number will not be listed on the sheet. A separate sheet indicating

what code represents the patient's name and medical record number will be kept in a secure location away from the data forms. Once completed, the data forms will be kept in [name] office at the MU site and in [name] office at the Florida site.

- b. There is no financial risk to the participants.

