Currently healthcare providers care for 2-3 patients in the NICU. To prevent alarm fatigue in our staff, we chose a wide range for our pulse oximeter alarms parameters to minimize the frequency of alarms. If they are in the middle of caring for another patient and another patient's saturations are only slightly out of range, they may take up to a few minutes to respond especially if the saturation level is high. This computerized system will be able to respond instantaneously whereby decreasing the risk for long-term complications. Currently no one knows for sure what the optimal saturation level range should be for preterm infants to prevent these long-term complications. Once we validate this device, we will be able to choose more narrow saturation levels to see if we can improve the outcomes of our patients.

10. Payment and Remuneration

- a. N/A

11. Costs

- a. There are no costs to the patients for this study. The grant will pay for the tubing needed to connect the high flow nasal cannula set-up or the bubble CPAP set-up to the study device.

12. Multiple Sites

- a. The University of Missouri Women's and Children's Hospital (Columbia, Missouri) is the lead site.
- b. All required approvals will be in place at each site prior to project implementation. The study will utilize a single IRB (sIRB). The Studer Family Children's Hospital at Ascension Health (Ascension Sacred Heart Pensacola) (Pensacola, Florida) will be an additional site for the study and will rely on the MU IRB for review. The MU IRB will be responsible for the oversight of the relying IRB.

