Cover Page

NCT04269161

NICU Oxygen Control Study

Statistical Analysis Plan

October 21, 2024

Statistical Design and Power

A crossover design was chosen because premature infants should have fewer events as they grow older each day, and a crossover design will mitigate this potential confounding effect. Furthermore, because every subject receives the device and the standard of care (nurse only), every subject serves as their own perfectly matched control. All subject-specific effects cancel out, so there is no concern for covariate imbalance. Finally, selection bias is minimized because all subjects receive all “treatments”. Nonetheless, the concealed allocation will be used with blocked randomization at each site, using sealed envelopes. The subjects will be randomized to group A or B in sets of 8 (i.e. in each group of 8 envelopes, 4 will be group A and 4 will be group B). During the entire study process the infants will receive normal NICU care and the parameters the SpO_2 range will be set by the physician caring for the infant. There are also built in manual overrides for the device, which allow the NICU staff to make changes while the subject is on the device phase of the study. The device will be able to record these changes and the staff will record their manual interventions in the study diary.

We have planned our sample size using a non-inferiority test for a 24 period, 2 treatment cross-over design, based on our primary endpoint, t_Δ . For a given patient, define $t_\Delta = (\text{mean elapsed time needed for device to re-establish } \text{SpO}_2 \text{ after alarm}) - (\text{mean elapsed time needed for nurse to re-establish } \text{SpO}_2 \text{ after alarm})$. The margin of non-inferiority will be chosen as $t_\Delta > -10 \text{ sec}$, so that a device which is no worse than 10 sec, on average than a nurse will be considered non-inferior. Assuming the standard deviation of $t_\Delta = 12$ and the true mean difference is zero under the alternate hypothesis, a sample size of 48 achieves 88% with $\alpha=0.05$. If there is 16% patient drop-out before crossover, so that the final $n=40$, the power drops to 82%. In all analysis, a (paired) t-test will be used. Our secondary endpoint will be analyzed in a similar manner. The secondary endpoint is the proportion of time SpO_2 is within the prescribed range, using an area-under-the-curve approach (with a discrete state) to account for varying time-on-test.

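### The primary endpoint pools high- and low-SpO2 alarms, so a device gain on high alarms could mask slower recovery from low SpO2

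*Protocol*

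**What the plan says.** Protocol section 7a defines the primary outcome as "Mean elapsed time needed to re-establish SpO2 within the desired range after an alarm". The SAP (Statistical Design and Power) makes this one difference per infant, t_delta. It starts from the "mean elapsed time needed for device to re-establish" SpO2 after an alarm and subtracts the corresponding nurse mean. The margin is explained as "so that a device which is no worse than 10 sec, on average than a nurse will be considered non-inferior". Neither document says which direction of alarm counts. Protocol section 8a describes monitoring in general terms: "If these vital signs fall out of the prescribed range, the monitor starts to alarm". On that description, both high and low SpO2 trigger alarms.

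The time-in-range secondary (protocol 7b and SAP) is a single in-or-out proportion. Protocol 7b also lists the frequency of apnea, bradycardia and desaturation events. That is the only planned outcome specific to low SpO2, and it counts events without timing recovery. The SAP gives no analysis for it.

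Three other statements bear on direction:

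- Protocol section 9, on staff who are busy with another patient when saturation is slightly out of range: "they may take up to a few minutes to respond especially if the saturation level is high".
- Protocol section 6, on the device, which turns the blender knob "to either increase or decrease the amount of oxygen being delivered to the patient by 2% every 10 seconds", provided the reading is considered reliable.
- Protocol section 4p, on overrides: "The bedside nurse will be able to switch the device to manual mode anytime she/he feels the oxygen concentration needs to be adjusted faster".

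**The concern.** The protocol's abstract names too much and too little oxygen as separate sources of harm, but the primary endpoint lets one offset the other. By the protocol's own account, nurses lose most time when SpO2 is high, so the device has most to gain there. Its rate limit, and the provision for staff to act faster, leave open whether it matches a nurse when SpO2 is low. If it does not, the gain on high alarms offsets the loss in the average.

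The trial could then declare non-inferiority for a device that brings infants back from low SpO2 more slowly than the margin allows, and no planned analysis would show it. Protocol 7b asks "Is our device safe to use on neonates", and a pooled result cannot answer that for low SpO2.

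**Working it through.** **The plan's own figure.** SAP inputs: margin 10 sec, SD of t_delta 12 (taken as seconds), true difference 0, alpha 0.05 with sidedness not stated, N=48, or 40 after dropout. Stated power is 88% and 82%.

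- A two-sample t-test with N/2 per group, one-sided 0.05, gives 88.5% (24+24) and 82.7% (20+20). This reproduces the plan.
- The paired t-test that the SAP names, with SD 12, gives more than 99.9% at n=48 and 99.98% at n=40. This does not.
- A paired test needs an SD of about 24 to give the stated power, so the checks below also show SD 24.

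**How pooling masks.** Let p be the share of alarms that are high, G the device's gain on high alarms (sec), and x its slowdown on low alarms (sec). With the same alarm mix in both modes,

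pooled difference m = (1-p)·x - p·G.

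Setting m = 0, the case the SAP assumes for its power, gives x = p·G/(1-p). The documents give neither p nor G, so both are assumed over a range.

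| p (high alarms) | x if G = 30 sec | x if G = 60 sec |
|---|---|---|
| 10% | 3.3 | 6.7 |
| 20% | 7.5 | 15.0 |
| 30% | 12.9 | 25.7 |
| 50% | 30.0 | 60.0 |

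For example, 0.3 × 60 / 0.7 = 25.7 sec, about 2.6 times the margin. With 10% high alarms, or with 20% and G = 30, the hidden slowdown stays inside 10 sec.

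**Probability of passing the pooled test.** Paired t-test, n=48, one-sided 0.05, intended direction (device not slower by 10 sec or more). The noncentrality is (10 - m)/(SD/√48). SD 12 is the SAP's value.

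| Low alarms | G | x | m | Pass, SD 12 | Pass, SD 24 |
|---|---|---|---|---|---|
| 70% | 60 | 30 | 0.7×30 - 0.3×60 = 3 | 99% | 64% |
| 70% | 30 | 20 | 0.7×20 - 0.3×30 = 5 | 88% | 41% |
| 80% | 60 | 20 | 0.8×20 - 0.2×60 = 4 | 96% | 53% |
| 90% | 60 | 15 | 0.9×15 - 0.1×60 = 7.5 | 41% | 18% |
| 90% | 30 | 15 | 0.9×15 - 0.1×30 = 10.5 | 3% | 4% |

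In every row the slowdown on low alarms exceeds the 10 sec margin.

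**Direction of the margin.** t_delta is device minus nurse, so a slower device gives a positive value. The SAP writes the criterion as t_delta > -10 sec. Taken literally, that becomes easier to pass as the device gets slower. The explanatory clause shows that the intended criterion is t_delta < +10 sec. A split by direction protects low alarms only once this is corrected.

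**Power of an added test on low alarms.** Paired, margin 10 sec, true difference 0, one-sided 0.05. The low-alarm SD is not in the documents.

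| SD (sec) | n=48 | n=40 |
|---|---|---|
| 12 | >99.9% | 99.98% |
| 18 | 98% | 96% |
| 24 | 88% | 83% |
| 30 | 74% | 67% |

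**The case against.** The strongest reply is that nothing in the documents says the device will be slower on low alarms. Protocol section 9 says the system can respond at once. The pilot (section 7d) reported a quicker return to range in automatic mode. The step limit applies to increases and decreases alike, so it also slows recovery from high SpO2. Comparing the device's ramp with a single turn of the knob leaves out the time before a nurse reaches the bedside. Staff are permitted, not instructed, to override, and no passage ties overrides to low SpO2. Eligibility rests partly on desaturation events, so low alarms may dominate, and masking is then weak.

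Most of this stands. A reader might infer that the protocol expects the two modes to differ in opposite directions. It does not: it supports only a larger nurse delay when SpO2 is high, which is a difference of degree. A reader might also infer that the interim efficacy rule is exposed in the same way. That rule asks for superiority by more than 20 sec, so a slowdown on low alarms can hide there only if p·G exceeds 20. The product is 0.3 × 60 = 18 and 0.5 × 30 = 15. It passes 20 only near the extreme of the assumed range (0.5 × 60 = 30), so early efficacy is not a sound part of this point.

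The reply does not remove the gap. The pilot had six infants, was not significant on this measure and is not reported by direction. A quick start says nothing about how long the correction takes. Nurses log desaturations and their resolution (section 4g), but the planned outcome is a count.

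**Conclusion.** The point holds as a cheap improvement to the analysis plan. Both endpoints that the SAP analyses merge high and low SpO2, and no planned analysis times recovery from low SpO2. A gain on high alarms could therefore mask a low-alarm slowdown beyond the 10 sec margin. At a pooled difference of 0 the hidden slowdown runs from about 3 sec (10% high alarms, 30 sec gain) to 60 sec (50%, 60 sec gain).

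That range rests on an assumed alarm mix and gain, and on the same mix in both modes. The pass probabilities also depend on the SD: 99% for a 30 sec slowdown with 70% low alarms and a 60 sec gain at SD 12, but 64% at SD 24. If 90% of alarms are low, a 15 sec slowdown passes at most 41% of the time in the cases shown. The calculations show what pooling permits. They are not evidence that the device is slower on low alarms.

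**What to change.** 1. Correct the sign first: with t_delta as device minus nurse, state non-inferiority as t_delta < +10 sec, and put the interim boundaries on the same convention.
2. From the stored SpO2 trace, compute t_delta separately for low and high alarms.
3. Keep the pooled test and also require the 10 sec margin to be met on low-SpO2 alarms. Both must pass, so alpha need not be split. Report high-alarm results alongside.
4. Report the share of time below range and the share above range separately.
5. State how infants with no low alarms in one of the modes are handled.

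No new data are needed, since SpO2 is already recorded continuously. The success rule becomes slightly stricter and each mean rests on fewer alarms. Power on low alarms is acceptable up to an SD of about 24 and falls to 74% / 67% (n=48 / n=40) at SD 30. Requiring the margin in both directions is a more debatable step: at SD 24, if the two tests were independent, joint power would be about 0.885² = 78% at n=48 and 0.827² = 68% at n=40. For that reason the added requirement is confined to low alarms.

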Cover Page

NCT04269161

NICU Oxygen Control Study

Statistical Analysis Plan

October 21, 2024

Statistical Design and Power

A crossover design was chosen because premature infants should have fewer events as they grow older each day, and a crossover design will mitigate this potential confounding effect. Furthermore, because every subject receives the device and the standard of care (nurse only), every subject serves as their own perfectly matched control. All subject-specific effects cancel out, so there is no concern for covariate imbalance. Finally, selection bias is minimized because all subjects receive all “treatments”. Nonetheless, the concealed allocation will be used with blocked randomization at each site, using sealed envelopes. The subjects will be randomized to group A or B in sets of 8 (i.e. in each group of 8 envelopes, 4 will be group A and 4 will be group B). During the entire study process the infants will receive normal NICU care and the parameters the SpO_2 range will be set by the physician caring for the infant. There are also built in manual overrides for the device, which allow the NICU staff to make changes while the subject is on the device phase of the study. The device will be able to record these changes and the staff will record their manual interventions in the study diary.

We have planned our sample size using a non-inferiority test for a 24 period, 2 treatment cross-over design, based on our primary endpoint, t_Δ . For a given patient, define $t_\Delta = (\text{mean elapsed time needed for device to re-establish } \text{SpO}_2 \text{ after alarm}) - (\text{mean elapsed time needed for nurse to re-establish } \text{SpO}_2 \text{ after alarm})$. The margin of non-inferiority will be chosen as $t_\Delta > -10 \text{ sec}$, so that a device which is no worse than 10 sec, on average than a nurse will be considered non-inferior. Assuming the standard deviation of $t_\Delta = 12$ and the true mean difference is zero under the alternate hypothesis, a sample size of 48 achieves 88% with $\alpha=0.05$. If there is 16% patient drop-out before crossover, so that the final $n=40$, the power drops to 82%. In all analysis, a (paired) t-test will be used. Our secondary endpoint will be analyzed in a similar manner. The secondary endpoint is the proportion of time SpO_2 is within the prescribed range, using an area-under-the-curve approach (with a discrete state) to account for varying time-on-test.

We will plan for one interim analysis to determine if the trial should be stopped early due to futility (strong evidence of inferiority, where a confidence interval for t_Δ lies entirely to the left of -10 and doesn't intersect -10) or for efficacy (strong evidence of superiority with margin $> +20 \text{ sec}$). This will be carried out when $n=32$ (16 subjects per site) is attained and stopping decisions will be based on O'Brien-Fleming stopping principles. The interim analysis will be carried out by an independent statistician on the University of Missouri's Data Safety and Monitoring Committee, which is also available to monitor the study for adverse events if requested by the IRB. In the event that the patient drop-out is greater than 16% before crossover, then a more complicated estimation procedure will be employed using mixed effects models; otherwise, complete cases will be used.

Assuming that the probability of enrollment for a given NICU patient is 10% (conservative est.), and because there are ≥ 6 new NICU patients/week at each hospital, we expect to enroll 48 patients and collect data in 43 weeks (11 months).

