- c. The primary healthcare team will determine the oxygen saturation parameters for the patient. The study team will adjust the computer set point goal for the oxygen delivery system to be the median of that range.
- d. If the patient meets criteria, we will approach the parents to give consent to enroll the infant in the study.
- e. Once consent is obtained, the study personnel will switch the infant to the equivalent study device for up to 6 days but the infant's interface with the device will not be changed. The infant will be kept on the same pulse oximeter as well.
- f. The bedside nurse and respiratory therapist will be educated on how the device works and what to do if they have any questions. A two-page information sheet will be hanging from the device, so they have a reference to look at. This information sheet includes a frequently asked questions section. It also reminds them to call the study team for any questions.
- g. The bedside nurse will be asked to keep a log of events that may be contributing to potential changes in oxygen needs or desaturation events such as changing diapers, being held, feeding, repositioning the infant, IV starts, blood draws, blood transfusions, medications administered, etc. In addition, acute events (apnea, bradycardia, desaturation) and their resolution will be documented on the logs. They will also document when the interface on the device is switched from a mask to prongs or vice versa or the settings are adjusted by the primary healthcare team (flow rate on the HFNC, PEEP on the bubble CPAP). They will also document anytime they had to switch the device the manual mode to adjust the FiO₂ faster than the computer was doing based on the infant's needs. They will then document when they switched the device back to the automatic mode to finish out the 6-hour period.
- h. Study personnel will collect the baby's medical history and mom's prenatal history. The baby's history including mom's prenatal history information produced by this study will be stored in the investigator's file and identified by a code number only. The code key connecting the baby's name to specific information about the patient will be kept in a separate, secure location in the investigator's office.

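### The primary endpoint is worded by who restored SpO2 (device or nurse) rather than by assigned mode, and no rule places alarms that end under a manual override

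*SAP*

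**What the plan says.** The SAP (Statistical Design and Power) defines t_Δ for each patient as the "mean elapsed time needed for device to re-establish" SpO2 after an alarm, minus the "mean elapsed time needed for nurse to re-establish" it. The same section provides for overrides in device periods: these "allow the NICU staff to make changes while the subject is on the device phase of the study". It adds that the device and the staff diary will capture them.

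The protocol's primary outcome (section 7a) names no actor: "Mean elapsed time needed to re-establish SpO2 within the desired range after an alarm". The question beneath it is put by mode: "Does the patient return to the prescribed saturation level range quicker in the automatic mode compared to the manual mode".

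Protocol section 4(p) leaves overrides to the nurse's judgement, with no time threshold: "The bedside nurse will be able to switch the device to manual mode anytime she/he feels" that oxygen must change faster than the computer is changing it. Section 6 describes the switch for the same purpose. Section 4(g) covers logging, "They will also document anytime they had to switch the device the manual mode", and has staff record the return to automatic for the rest of that 6-hour period.

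Neither document says which term of t_Δ an overridden alarm belongs to, when its clock stops, or whether it is excluded. The SAP's only data-handling rule concerns patients who drop out.

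**The concern.** An automatic period can contain alarms that a nurse resolved. Under the SAP's literal wording, such an alarm is not time the device needed, so an analyst could reasonably leave it out of the device mean or count it in the nurse mean. The trigger for an override is the nurse's view that the device is too slow, so leaving these alarms out is plausibly linked to the outcome being measured. If the overridden alarms are mostly the slow ones, the device mean loses its worst values.

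At stake is the non-inferiority conclusion. The margin is 10 sec and the planning SD is 12 sec, so a shift of a few seconds, arising only from how these alarms are classified, could decide the test.

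**Working it through.** **Inputs from the SAP.** Margin 10 sec; SD of t_Δ 12; true difference 0 under the alternative; α = 0.05, sidedness not stated; n = 48, falling to 40 with 16% drop-out; paired t-test; stated power 88% and 82%.

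**Step 1: the plan's own figures.** A two-sample t calculation with n/2 per sequence, one-sided 0.05, has noncentrality 10 / (12 × √(4/n)). This is 2.887 at n = 48 and 2.635 at n = 40, giving power of 88.5% and 82.7%, which matches the SAP. The paired t-test that the SAP names, with SD 12, gives more than 99.9% at both sizes and would need an SD of about 24 to match. The power figures are not the issue here, but step 2 therefore shows both SDs.

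**Step 2: what a small shift does.** Suppose the device is truly 10 sec slower, exactly at the margin, and classification makes it look b sec better, with the SD unchanged. The pass probability is P(T > t₀.₉₅,ₙ₋₁), where T is noncentral t with n − 1 degrees of freedom and noncentrality b√n/SD. At n = 48 and SD 12 that is b × 6.928/12 = 0.577b, and the critical value is 1.678.

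| Shift b (sec) | Noncentrality (n = 48, SD 12) | n = 48, SD 12 | n = 40, SD 12 | n = 48, SD 24 |
|---|---|---|---|---|
| 0 | 0 | 5% | 5% | 5% |
| 1 | 0.577 | 14% | 13% | 9% |
| 2 | 1.155 | 31% | 27% | 14% |
| 5 | 2.887 | 88% | 83% | 41% |

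Here, toward the device follows the SAP's verbal intent, that the device be no more than 10 sec worse. The inequality as written, t_Δ > −10, does not fit a difference taken as device minus nurse.

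**Step 3: can classification move the estimate by that much?** The documents give no recovery times or override rates, so everything in this step is assumed.

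*One worked case.* Device-alone recovery is lognormal with mean 60 sec and log-SD 1, so the log-mean is ln 60 − 0.5 = 3.594. The nurse overrides every alarm unresolved at 120 sec.
- Share overridden: P(X > 120) = 1 − Φ((ln 120 − 3.594)/1) = 1 − Φ(1.193) = 11.6%.
- Overridden alarms dropped: E[X | X < 120] = 34.6/0.884 = 39.2 sec, which is 20.8 sec below 60.
- Overridden alarms kept with their actual return to range, r sec after the override: 34.6 + 0.1164 × (120 + r). This gives 50.9 sec at r = 20, 55.5 at r = 60, 60.0 at r = 98 and 62.5 at r = 120.

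*Direction under other patterns.* Simulated gamma (shape 2) times, manual mean 60 sec, device-alone mean 70 sec (true difference +10), nurse recovery after override averaging 20 to 120 sec. Estimated differences in seconds:

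| Handling | Late overrides (at 60 sec if unresolved; 5–25% of alarms) | Early overrides (at 5 sec, unrelated to severity; 10–50%) |
|---|---|---|
| Dropped | +8 to −2 | +9.4 to +10.0 |
| Moved to nurse, full elapsed time | +7 to −26 | +21 to −12 |
| Moved to nurse, timed from override | +10 to −14 | +23 to −11 |
| Kept in assigned period | +3 to +28 | +37 to −12 |

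Values below +10 flatter the device against its device-alone performance; values above penalise it. With late overrides, dropping favours the device throughout and moving does so in all but negligible amounts. With early overrides, dropping is almost neutral and moving can go either way.

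**The case against.** The strongest reply is that device and nurse are simply the SAP's treatment labels. The SAP describes the comparison as the device against nurse-only standard of care and refers to a device phase. The protocol asks by mode, and an overridden infant goes back to automatic within the same period. On that reading t_Δ is already a comparison by period. This is a reasonable reading, and it stands to this extent: a reader might infer that the plan directs rescued alarms to be dropped or moved, and the documents say no such thing. They are silent. What the reply does not do is settle an alarm that starts in automatic and ends in manual, because the mode itself changes before the alarm resolves.

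A reader might also infer that every way of handling these alarms biases the test toward the device. The working does not support that. Overrides have no time threshold, early ones can be neutral or unfavourable to the device, and keeping alarms in their assigned period can move the estimate either way.

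Nor is counting by assigned mode itself a bias. It is the correct quantity for automatic mode with override available, which is how the protocol puts its question. It becomes a concern only if the result is then presented as what the device does unaided.

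**Conclusion.** The concern holds as a gap in the definition of the primary endpoint: the SAP's wording goes by actor, the protocol's by mode, overrides are provided for, and no rule assigns the alarms they end. Taken literally, the SAP wording would remove or reassign alarms for a reason tied to the outcome. Bias toward the device is plausible, because overrides follow perceived slowness, but it is not certain.

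The sensitivity of the test to a shift rests on the SAP's own figures plus a one-sided 0.05 reading of α. At SD 12 and n = 48, 1, 2 or 5 sec takes the 5% error at the margin to about 14%, 31% or 88%; at SD 24, 5 sec still gives 41%. Whether a shift of that size would occur rests on assumed override and recovery patterns and cannot be established from the documents. The gap should be closed before the analysis.

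**What to change.** 1. Define t_Δ by assigned mode: mean time from alarm to actual return to range over every alarm that starts in a period assigned to automatic, minus the same for periods assigned to manual. Drop or move no alarm because of an override. Analyse the secondary endpoint, proportion of time in range, the same way.
2. State that this estimates automatic mode with override available, and that it can mask a deficit of the device alone.
3. Report overrides per automatic hour.
4. Add a sensitivity analysis that does not credit the nurse's rescue to the device, for example by censoring overridden alarms at the override or counting them as failures over a range of pre-specified penalty times. Censoring here is unlikely to be independent of recovery time, so the penalty range should carry more weight. A single penalty equal to the infant's longest automatic-mode time is not enough: in the worked case with r = 20, that time is 140 sec and the mean is again 50.9 sec, the same as crediting the rescue.
5. Limit any device-alone claim to results that hold in that analysis.

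The cost is SAP wording, one extra analysis and a somewhat more cautious device-alone claim. The device, diary and bedside log are already meant to record overrides, so no new data collection is needed.
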